#### Reasons:

- For each add-on PD medication/therapy at the time points LCIG initiation and at 3, 6, 9, and 12 months after LCIG initiation and at visit::
  - Reason for start (multiple answers)
  - If not ongoing: reason for discontinuation (multiple answers)
- Reason for change on LCIG dose in general
- Reason for LCIG dose changes (multiple answers) by 5%, 10%, 15%, 20% or 25% or higher
- Reason for substantial LCIG dose changes (multiple answers) with substantial change defined as any increase or decrease of the total daily LCIG dose by more than 20%
- Latency and duration of treatments:
  - For patients with add-on PD medication or PD therapy at LCIG initiation: Time from LCIG initiation until LCIG is given as a monotherapy (separately for monotherapy 1 and monotherapy 2 definition)

[figure not shown]
Only patients with add-on PD medication or PD therapy at LCIG initiation

 For patients with add-on PD medication or PD therapy at LCIG initiation and separately for patients with and without ongoing monotherapy at visit: Duration of LCIG monotherapy (separately for monotherapy 1 and monotherapy 2 definition) Only patients with add-on PD medication or PD therapy at LCIG initiation Analysis a) Without ongoing monotherapy until visit

Analysis b) With ongoing monotherapy until visit

- For each add-on PD medication/therapy:
   Time from LCIG initiation until the respective add-on PD medication/therapy is started or changed
- Time from LCIG initiation until the first LCIG dose change by 5%, 10%, 15%, 20% or 25%
- Time from LCIG initiation until the first substantial LCIG dose change with substantial change defined as any increase or decrease of the total daily LCIG dose by more than 20% in relation to first LCIG infusion
- LCIG monotherapy (1 and 2) vs. LCIG plus add-on PD medication:
  - o HCRU:
    - Primary occupation (retired, on sick leave, unemployed, working full time, working part-time, student)
      - If retired: due to PD (yes, no)
      - If on sick leave: due to PD (yes, no)
      - If unemployed: due to PD (yes, no)
    - Permanent living in a nursing home/institution (yes, no)
    - Help in daily activities
    - Frequency of visits:
      - General practitioner

- Nurse
- Occupational/speech therapist
- Physiotherapist
- Psychologist and/or psychiatrist
- Dietician
- Discussion of LCIG monotherapy (yes, no, patient did not remember)
- Offering of LCIG monotherapy (yes, no, patient did not remember)
- Number of pills in addition to LCIG the patient would be willing to take each day
- Problems before starting LCIG (multiple answers)
- Help required to remember to take the medication (yes, no)
- Influence on the patient's decision to start treatment with LCIG (yes, no, missing)
  - If not 'no':
    - Doctor
    - Caregiver
    - Other family member
- Any scheduled visits with the treating physician for PD (yes, no)
- Any extra or unscheduled visits with the treating physician for PD (yes, no)
- Been seen in the Emergency Room due to PD (yes, no)
- Hospitalization (yes, no)
  - If yes: due to PD (yes, no)
- Overall treatment preference from physician's profile (LCIG as monotherapy, LCIG plus add-on PD medication)

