To assess the generalizability of the data from the patients enrolled, the physician will be asked to document on a separate Case Reporting Form the number of patients who are eligible but refuse to participate in the study. Only age ranges (<30 years, 30-45 years, 45-65 and > 65 years) and reason(s) for not participating will be collected.

The primary endpoint of this PMOS will be the percentages of APD patients on LCIG monotherapy right after LCIG initiation and at 3, 6, 9, and 12, respectively.

The secondary endpoints are:

- Descriptive data from patient's PD medication:
 - For add-on PD medication: percentage of patient on each PD medication (by drugs and class), total daily dose and levodopa equivalent Daily dose (LEDD), posology (number of times per day);
 - For LCIG infusion settings and substantial dose adjustments: total dose per day and specific for each type of dose (morning dose and continuous dose) and number of hours of infusion.

- Tapering process: number of days required for the tapering process, total dose per day and posology for add-on PD medication prior to LCIG initiation, at LCIG initiation (titration) or during ongoing LCIG treatment
- Main reasons for introduction or tapering of add-on PD medication or LCIG substantial dose adjustments
- Latency and duration of treatments data:
 - Number of days or months from LCIG initiation until LCIG is given as a monotherapy and the duration of LCIG monotherapy.
 - Number of days or months from LCIG initiation until the introduction or tapering of each PD medication, or until any LCIG substantial dose adjustments.
- LCIG monotherapy vs LCIG plus add-on PD medication data:
 - Healthcare Resource Utilization, as measured by Healthcare Resource Utilization Questionnaire (HCRU)
 - Patient's, caregiver's, and physician's overall preference on LCIG monotherapy vs. LCIG plus add-on PD medication, percentage of patient's and physician's preference for each of the options
 - Predictors for LCIG as monotherapy vs. LCIG plus add-on PD medication based on the patient's profile, including socio-demographics, clinical status (motor and non-motor symptoms), Levodopa-equivalent dose (LED), PD medication and Quality of Life
 - Predictors for LCIG as monotherapy vs. LCIG plus add-on PD medications based on the physician's profile including experience as measured by number of years on APD patient management, number of years using LCIG therapy, and number of patients on LCIG therapy

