9.2.7.5 Previous PD medication and add-on PD treatment during **LCIG Treatment**

Data on previous PD medication (right before initiation of LCIG treatment) will include date of drug initiation and/discontinuation, reason for its discontinuation, drug name, total dose per day, posology, and attempts of previous device-aided therapies (e.g., CSAI, DBS).

Data on add-on PD medication upon LCIG initiation or during LCIG treatment will include date of drug initiation/discontinuation, drug name, total dose per day, posology, tapering* process (duration and posology), starting and end date of LCIG titration, reasons for add-on drug therapy (severity and frequency), timing of add-on drug (during/outside of infusion hours).

Levodopa equivalent daily dose (LEDD) table published by Tomlinson, et al will be used to calculate LEDD. [47]. Each PD medication amount should be multiplied by the appropriate value to obtain the corresponding LEDD. Adding together the corresponding LEDD for each PD medication, will be providing the total LEDD.

9.2.7.6 **Concomitant Disease and Medication**

Information on concomitant disease and medication (non-PD treatment) will be collected and reported in the eCRF, including drug name, indication, start/stop date, and dosages.

^{*}The term "tapering" is used within this study in the context of drug treatment. It refers to the process of reducing a certain drug dosage incrementally (over a few days or weeks), instead of its abrupt discontinuation. For some PD medications a tapering process is needed to avoid a withdrawal syndrome

9.2.7.7 **LCIG Treatment**

Information on LCIG treatment from initiation until the day of the visit will be documented in the eCRF, including reason(s) for initiation of LCIG treatment, date of introduction of LCIG, use of nasojejunal tube, date of PEG-J procedure, date of titration and duration of titration process, infusion settings (infusion time, morning dose, continuous infusion rate, total daily dose) and dose modification (number of dosage changes, new infusion settings or temporary interruptions in LCIG daily infusion rate and reasons for dosage adjustment).

A LCIG substantial dose adjustment is defined as any increase or decrease of the total daily LCIG dose by more than 20% of total daily dose.

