#### 4.2.1 Inclusion criteria

Patients were eligible for study participation if all of the following criteria were fulfilled:

- 1. Patients diagnosed with APD and on LCIG treatment for at least 12 months
- 2. Patient must have been on continuous LCIG treatment for at least 80% of days in the preceding year
- 3. Patients must be treated by the same physician (PI or co-investigator) since the initiation of LCIG treatment
- 4. Decision to treat with LCIG was made and therapy was started by the physician prior to any decision to approach the patient to participate in this study
- 5. Prior to any data collection, the patient, or legal authorized representative (LAR) has voluntarily signed an Authorization for Use/Disclosure of Data (AUDD)/informed consent form (ICF) according to national regulations after the study has been explained and the subject has had the opportunity to have questions answered

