#### 6.4 Primary variable

There are two primary variables:

1. LCIG monotherapy 1 (yes, no) at LCIG initiation and at 3, 6, 9, and 12 months after LCIG initiation

with the following definition:

- LCIG monotherapy means that the patient is not on any add-on PD medication or PD therapy at the respective time point.
- 2. LCIG monotherapy 2 (yes, no) at LCIG initiation and at 3, 6, 9, and 12 months after LCIG initiation

with the following definition:

LCIG monotherapy means that the patient is allowed to take an add-on PD medication or PD therapy at the respective time point, however, only in the evening after the LCIG infusion is completed (i.e. reason for start of add-on PD medication: other).

Additional specifications for both variables are:

- Medications for indications secondary to PD are allowed.
- If the reason for add-on PD medication is missing the medication will be considered as taken during LCIG infusion (i.e. no monotherapy).
- LCIG initiation date is the start date of the first LCIG infusion.
- 3 months after LCIG initiation is calculated as LCIG initiation date + rounded (3 [months] x 30.4 [days]). 6, 9, and 12 months after LCIG initiation will be calculated analogously.
- For LCIG initiation date with missing day the 15th will be used.

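### Reasons for starting and stopping add-on PD drugs are tabulated only at six dates, with no reference date for "If not ongoing: reason for discontinuation (multiple answers", so no table reports each start and stop once in the period when it happened

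*SAP*

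**What the plan says.** Protocol 9.1 lists as a secondary endpoint "Main reasons for introduction or tapering of add-on PD medication or LCIG substantial dose adjustments". Protocol 8.0 also sets an objective on the reasons that justify PD drug use before LCIG, at initiation and during long-term treatment.

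SAP 6.5, under Reasons, specifies the tabulation as "For each add-on PD medication/therapy at the time points LCIG initiation and at 3, 6, 9, and 12 months after LCIG initiation and at visit", with two items beneath it: "Reason for start (multiple answers" and "If not ongoing: reason for discontinuation (multiple answers" (both allow several answers).

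Four neighbouring provisions matter:

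- SAP 6.5 plans further time points between month 12 and the visit for add-on use and for LCIG infusion settings. The Reasons list for add-on drugs does not include them.
- In the same Reasons block, reasons for LCIG dose changes are not tied to fixed dates.
- The latency items in SAP 6.5 use actual dates for add-on starts and changes but carry no reasons. SAP 6.3 lists stop reasons only for therapies ended before LCIG was considered.
- Dates exist in the data. Protocol 9.2.7.5 states: "Data on add-on PD medication upon LCIG initiation or during LCIG treatment will include date of drug initiation/discontinuation".

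**The concern.** A start or a stop happens on one day. A table drawn at fixed dates describes a state on those dates. It can answer which drugs patients were taking and why they were taking them then. It does not directly answer why drugs were introduced or withdrawn, or in which phase of treatment.

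The line on stop reasons adds a second difficulty. A drug in use on a given date is ongoing on that date, so the words about not being ongoing must refer to some other date, and the SAP gives none. Two programmers could produce different tables from the same text.

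At stake is a gap that the protocol itself sets out to fill. Its background says the earlier multinational registry collected nothing on the rationale for introducing, tapering or maintaining add-on drugs.

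**Working it through.** The plan states no figure on this point, so there is none to reproduce. The check has two parts: what each reading of the text would report, and how large the gap is under the reading that loses events.

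**Inputs from the documents**

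- Dates: SAP 6.4 gives "3 months after LCIG initiation is calculated as LCIG initiation date + rounded (3 [months] x 30.4 [days" and applies the same rule to the later months. Rounding 3, 6, 9 and 12 times 30.4 gives days 91, 182, 274 and 365. With day 0, the gaps are 91, 91, 92 and 91 days.
- Follow-up: SAP 4.2.1 requires "Patients diagnosed with APD and on LCIG treatment for at least 12 months" and sets no upper limit, so the gap from month 12 to the visit is open-ended.

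**Assumptions (the documents give no values)**

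- Spell lengths *d*, visit dates and uniformly distributed start times.

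**The two readings**

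Reading A: each table covers drugs in use at the date, and the stop reason is shown if the drug was stopped at any later time. Reading B: a stop reason is shown if the drug had already been stopped by the date.

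| Course of the add-on drug | Reading A | Reading B |
|---|---|---|
| Starts month 4, stops month 5 | Neither reason reported | Stop reason at months 6, 9, 12 and visit (4 tables) |
| Present at initiation, stops month 10 | Stop reason at initiation and months 3, 6, 9 (4 tables, all before the stop) | Stop reason at month 12 and visit (2 tables) |
| Starts and stops between month 12 and the visit | Neither reason reported | Stop reason at the visit (1 table) |
| Present from initiation to visit | Start reason in all 6 tables | No stop reason |

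Under A the visit table can hold no stop reasons, because a drug in use at the visit has not been stopped.

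**Size of the gap under Reading A**

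A spell of *d* days that starts uniformly in a gap of *G* days touches no table date with probability max(0, 1 - *d*/*G*).

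- Quarterly gap, *G* = 91: *d* = 14 gives 1 - 14/91 = 0.85; *d* = 30 gives 0.67; *d* = 60 gives 0.34; *d* = 90 gives 0.01 (0.02 for the 92-day gap).
- Month 12 to visit, *G* = 365: 0.92 for 30 days, 0.75 for 90 days, 0.51 for 180 days.
- Month 12 to visit, *G* = 730: 0.96, 0.88 and 0.75 for the same lengths.

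Over the whole follow-up of *V* days, the share missed is the sum over gaps of max(0, *G* - *d*), divided by *V*. For a 90-day spell the four quarterly gaps contribute 1 + 1 + 2 + 1 = 5 days.

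- Visit at day 366: 5/366 = 1%.
- Day 730: (5 + 275)/730 = 38%.
- Day 1096: (5 + 641)/1096 = 59%.
- Day 1826: (5 + 1371)/1826 = 75%.

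For spells of about three months, then, almost all of the loss comes from the stretch after month 12.

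**Size under Reading B**

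No spell with usable dates is lost. A stop before month 3 appears in 5 tables, and a stop between months 9 and 12 appears in 2. The visit table would hold every stop, but without the period in which it happened.

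**The case against.** The strongest reply is that the text does not say the tables are limited to drugs in use at each date. Reading B gives the line on stop reasons a meaning at every time point, including the visit. Under it, between-date spells are captured and the percentages above do not apply. This stands: loss of events is one possible consequence of the wording and is not established by it. It does not rescue the table, because Reading B repeats each stop reason at every later date. Recovering the period by subtracting successive tables would need a per-episode count, and the SAP gives no counting rule for reasons. The once-per-patient rule in SAP 7.6 concerns therapy types.

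A reader might infer that long-running drugs are counted several times in one distribution, so that the reported mix of reasons leans towards drugs that were kept. The documents do not support that. The repetition is across separate time-point tables, and no pooled table is planned. For the objective on reasons that justify use, showing a continuing drug's reason at each date is appropriate.

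The percentages are also conditional. They describe short spells that fall inside a gap and do not estimate the share of all starts or stops. Drugs in use at LCIG initiation are at a table date and are included under either reading.

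Finally, the endpoint is descriptive and secondary, the dates stay in the database, and SAP 7.10 permits extensions. That limits the weight of the point. However, SAP 7.10 specifies no event-based table, and SAP 2.5 makes the written methods binding for programming.

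**Conclusion.** The point holds as a mismatch between an event endpoint and a fixed-date tabulation, made worse by an undefined reference date. Under neither reading is each add-on start and each stop reported once in the period when it occurred.

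How much is missing depends on the reading. Under A, with uniform start times, between-date spells are missed at the quarterly rates shown, from about two thirds at 30 days to almost none at 90 days, and at higher rates after month 12. Under B there is repetition and no loss. It would go too far to conclude that short, failed trials of add-on drugs are certain to vanish, or that the study's results on reasons are biased: the first requires Reading A, and the second requires a combined mix that the SAP does not plan. No primary estimate or regression uses this table.

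**What to change.** Add one table set to SAP 6.5 that counts each add-on start once and each stop once, from LCIG initiation to the visit, with its reasons, by drug and class. Place each event in the interval of its recorded date: initiation/titration, 0-3, 3-6, 6-9, 9-12 months, and after 12 months. State where titration ends and the 0-3 month interval begins; SAP 6.3 already uses the date on which titration was finalised. Include an interval-unknown row for incomplete dates, because SAP 6.4 imputes only a missing day of LCIG initiation and the tapering rule in SAP 6.5 leaves incomplete dates unimputed.

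Keep the fixed-date tables for the percentage on each drug and for the reasons for current use, and define ongoing in them by reference to a stated date.

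The cost is SAP wording and one more table set to program. No new data are needed: start and stop dates are collected under Protocol 9.2.7.5, and the SAP already presupposes recorded start and stop reasons. The downside is that some events with incomplete dates cannot be placed in an interval, though they will still be counted.

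### Latency to monotherapy 2 (SAP 6.5) starts from patients with any add-on at LCIG initiation, a group that can include patients already on monotherapy 2 at day 0

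*SAP*

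**What the plan says.** SAP 6.5, under latency and duration of treatments, sets the measure for both definitions: "Time from LCIG initiation until LCIG is given as a monotherapy (separately for monotherapy 1 and monotherapy 2 definition"). The same sentence opens by naming one group for both: "For patients with add-on PD medication or PD therapy at LCIG initiation: Time from LCIG initiation until LCIG is given as a monotherapy". A further line repeats the restriction without splitting it by definition: "Only patients with add-on PD medication or PD therapy at LCIG initiation". The duration of monotherapy is analysed in the same group.

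SAP 6.4 gives the two definitions. For monotherapy 1, "LCIG monotherapy means that the patient is not on any add-on PD medication or PD therapy at the respective time point". For monotherapy 2, "LCIG monotherapy means that the patient is allowed to take an add-on PD medication or PD therapy at the respective time point", but "only in the evening after the LCIG infusion is completed (i.e. reason for start of add-on PD medication: other"). Monotherapy 2 is classified from day 0 onwards: "LCIG monotherapy 2 (yes, no) at LCIG initiation and at 3, 6, 9, and 12 months after LCIG initiation". The initiation date is the start of the first LCIG infusion. A missing reason for an add-on counts as no monotherapy.

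The protocol (section 8.0) and SAP 3.2 list latency from LCIG initiation to monotherapy as a secondary objective and do not limit it to patients with an add-on. Protocol 9.2.7.7 defines monotherapy by what is taken during infusion hours, so monotherapy 2 is the closer of the two SAP variables to the protocol's own definition.

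**The concern.** The starting group of a latency should contain people who have not yet reached the state being timed. For monotherapy 1, having an add-on at initiation guarantees this. For monotherapy 2 it does not, because some add-ons are compatible with monotherapy 2. Patients whose only add-on is taken after the infusion enter the analysis with nothing left to reach.

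The summary would then mix two things: the time taken by patients who had to change something, and zeros from patients who did not. Anyone using the monotherapy 2 latency to see how quickly daytime add-ons are given up after LCIG starts would get too short an answer, and the shortfall would depend on how common evening-only add-ons are, not on the speed of change. The duration analysis carries the same feature: for these patients the monotherapy 2 spell begins at day 0.

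**Working it through.** The plan states no figure for latency, so there is none to reproduce. The check sets the rules side by side and then shows what zeros do to the planned summaries.

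**Step 1: who is in the group, and who already meets the definition at day 0 (SAP 6.4 and 6.5).**

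| Status at LCIG initiation | In the latency group? | Already on monotherapy 1? | Already on monotherapy 2? |
|---|---|---|---|
| No add-on | No | Yes | Yes |
| Add-on after the infusion only | Yes | No | Yes |
| Any add-on during the infusion, or reason missing | Yes | No | No |

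For monotherapy 1, the group is exactly the patients not yet on it. For monotherapy 2, the middle row is in the group although already on it, and the top row is left out although its monotherapy 2 status is the same.

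**Step 2: is there a rule that removes the middle row?** None is visible. SAP 6.5 does not exclude these patients, set them to missing or report them separately. SAP 6.7 covers only missing questionnaire items. SAP 7.1 and 7.6 add nothing on latency. SAP 2.5 makes the written methods mandatory for programming.

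**Step 3: the value these patients get.** Time from initiation to a state held at initiation is 0 days. SAP 6.3 adds 1 to several other durations. No convention is stated for latency; with +1 every value rises by one day, including the zeros.

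**Step 4: effect on the planned summaries.** SAP 7.1 lists mean, quartiles and median. Let q be the share of analysed latencies that are zeros, and T the mean latency in the remaining patients. Then:

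- mean = q × 0 + (1 − q) × T = (1 − q)T, for any distribution;
- lower quartile = 0 once q ≥ 25%, and median = 0 once q ≥ 50%.

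The documents give neither q nor T. Assume T = 90 days and an exponential shape. For q below 50%, median = T × ln(2(1 − q)). For q below 25%, lower quartile = T × ln((1 − q)/0.75).

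| Assumed q | Mean (days) | Median (days) | Lower quartile (days) |
|---|---|---|---|
| 0% (after the fix) | 90 | 62.4 | 25.9 |
| 10% | 81 | 52.9 | 16.4 |
| 20% | 72 | 42.3 | 5.8 |
| 30% | 63 | 30.3 | 0 |
| 40% | 54 | 16.4 | 0 |
| 50% | 45 | 0 | 0 |

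The proportional change is the same for T = 30 or T = 180 days. For example, at q = 30% the mean is 21 instead of 30, or 126 instead of 180.

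**Step 5: q refers to analysed values, not to the whole group.** No censoring method is stated for latency, so patients who never reach monotherapy 2 may have no value. If, as an assumption, 20% of the group were evening-only and 40% of the other 80% ever reached monotherapy 2, then q = 0.20 / (0.20 + 0.80 × 0.40) = 0.20 / 0.52 = 38%.

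**The case against.** **The zero is inferred.** The SAP does not say that these patients score 0 days. A figure beside the rule could not be read in the copy reviewed and may show how the time is counted. A programmer might also set such patients to missing. This stands as a limit on certainty. But the text on both sides of the figure gives one restriction for both definitions, and 0 days is what the written definitions yield.

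**The size is unknown.** A reader might infer a large effect from the Italian interim report cited in Protocol 7.0, with oral levodopa use of 5% by day and 26% at night. The documents do not support that step. Those figures come from another study, describe use during treatment (mean 14 months) and cover one drug class. They do not give the share of patients at the first infusion with only after-infusion add-ons. Protocol 7.0 also says that other therapies are usually tapered during a titration period, so daytime add-ons may be more common at day 0 than later. The report shows only that night-time use occurs. This objection stands in full.

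**The planned output would partly reveal it.** Monotherapy 1 and 2 are both reported at initiation, and the difference between the two counts is the number of add-on patients already on monotherapy 2. The minimum and lower quartile would also show a cluster of zeros. Tapering time per drug and time to first change of each add-on are analysed separately, so this median is not the planned measure of tapering speed. This stands in part. If the zeros are recorded as such, a reader could recover the mean by dividing by (1 − q), but not the median.

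**Zero may be the right value.** The objective is unrestricted, and for a patient on monotherapy 2 from the start, 0 days is the true latency. One common group also lets the two definitions be compared in the same patients. But an all-patients target would need the day-0 patients without an add-on as zeros too, and the SAP leaves them out. A transition-only target would leave out the evening-only patients, and the SAP keeps them. The rule fits neither.

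**Conclusion.** The point holds as an inconsistency between SAP 6.4 and SAP 6.5. The group chosen for the monotherapy 2 latency can contain patients already on monotherapy 2 at the time origin, and no visible rule removes them.

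The direction is certain wherever such patients are analysed with their latency of zero: the mean falls by the fraction q, the lower quartile is 0 from q = 25%, and the median is 0 from q = 50%. The size is not established. Every value of q and T in the table is an assumption, and the result also rests on the 0-day value that the definitions imply but the SAP does not write down. Evening-only status depends on the recorded reason for the add-on, so misclassification would change the number of zeros but not the mechanism.

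A reader might conclude that the planned latency is badly wrong, or that the primary result is affected. The documents support neither. The primary percentages do not use this group, and the latency is a descriptive secondary summary with no test attached, in a study that SAP 7.10 calls exploratory. It is still worth correcting before programming, because latency is a stated objective and the correction is small.

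**What to change.** In SAP 6.5, replace the common restriction by one for each definition:

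- Latency to monotherapy 1: patients not on monotherapy 1 at LCIG initiation.
- Latency to monotherapy 2: patients not on monotherapy 2 at LCIG initiation.
- Beside each latency, report the number and percentage already on that monotherapy at initiation.
- For the duration of monotherapy 2, use the same group, or state that spells may start at day 0.

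The cost is a few lines of SAP text and one filter in the program. No new data are needed, because SAP 6.4 already derives both statuses at initiation. The price is a smaller monotherapy 2 group and two latencies that no longer refer to the same patients. If comparison in the same patients is wanted, the present common-group result can be kept as an additional table, labelled as including patients already on monotherapy 2 at day 0.
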